1.4.1 Discussion

Patients entering this trial will already have received a benefit from treatment with spesolimab in a preceding trial. This, in addition to the medical need for effective and well tolerated drug specifically and directly treating the structural aspects of CD makes it conceivable to anticipate that the benefits of receiving further treatment will outweigh the risks in these patients. Moreover, since there are no mechanism- or compound-related safety alarm signals from all above mentioned data from spesolimab, it is highly likely that eligible patients for the study, CD patients with perianal fistulising disease, will not be exposed to undue risks and adverse events.

The benefit-risk profile is thus considered appropriate for an experimental therapy at this stage of clinical development.

Benefit-Risk Assessment in context of COVID-19 pandemic.

BI 655130 is an immune-modulating humanized monoclonal antibody that blocks the human IL-36 receptor and thereby the pro-inflammatory IL-36 pathway. Available non-clinical and clinical data have not shown an increased risk of infections with BI 655130. However, similar to other immune modulating biological treatments, BI 655130 may hypothetically increase the risk of infections. Risk mitigation measures, such as exclusion of patients with increased risk of infections, close monitoring of adverse events, as well as guidance on treatment and handling of acute infections occurring during the trial are described in the clinical trial protocol. As any other acute infection, a suspected or diagnosed COVID-19 infection should be treated according to the standard of care and interruption of study medication should be considered.

Currently, information about the immune response in patients with COVID-19 is sparse and inconclusive. There are some reports suggesting high-levels of pro-inflammatory cytokines in the severe cases, with much of the morbidity associated with coronavirus infection, potentially related to immune activation and inflammation. To date, there is no reliable evidence suggesting a link between SARS-CoV-2 infections and the IL-36 pathway targeted by BI 655130. Considering the current knowledge of COVID-19 and the implemented risk mitigation measures addressing the potential risk of infections, patients studied in trials with BI 655130 are not believed to be at higher risk of COVID-19 due to their background or concomitant diseases. Protocol-defined procedures do not impose undue risk to study participants. The benefit-risk assessment of BI 655130 remains favourable in the context of the COVID-19 pandemic.

To address potential risks associated with operational aspects related to the participation in clinical trials in context of COVID-19 pandemic, different risk mitigation measures are considered in ongoing and planned BI 655130 clinical trials based on local requirements and development of pandemic.

The investigators will take the totality of information related to each single patient and the local COVID-19 situation into consideration when performing the individual benefit-risk assessment on a case-by-case basis. Considering all aspects, the investigator will decide upon each patient's (continued) participation in the planned trials. BI as the sponsor, where required, will support the investigator in their decision finding.

2. TRIAL OBJECTIVES AND ENDPOINTS

2.1 MAIN OBJECTIVES, PRIMARY AND SECONDARY ENDPOINTS

Table 2.1:1 Definitions of Study Outcomes

perianal fistula remission	closure of all external openings, no drainage / discharge despite gentle finger compression, that were open and draining at baseline (BL) of parent trial and closure of all external openings that were newly emerged during the parent trial or this trial
perianal fistula response	closure and no drainage /discharge despite gentle finger compression of at least 50% in number of external openings regardless of the onset time, compared with the number of open and drainage fistulas at baseline of parent trial

2.1.1 Main objectives

1. To evaluate the long-term **safety** of spesolimab in patients with perianal fistulising Crohn's disease who have completed treatment in parent trials
2. To evaluate the long-term **efficacy** of spesolimab in patients with perianal fistulising Crohn's disease, who have completed treatment in parent trials

2.1.2 Primary endpoint(s)

Exposure adjusted rate of patients reporting a treatment emergent adverse event (TEAE) up to week 336 of maintenance treatment

2.1.3 Secondary endpoint(s)

- Proportion of patients with perianal fistula remission at weeks 48, 96, 144, 192, 240, 288, and 336
- Proportion of patients with perianal fistula response at weeks 48, 96, 144, 192, 240, 288, and 336

Further details on the planned analyses are given in [Section 7.3](#).

3. DESCRIPTION OF DESIGN AND TRIAL POPULATION

3.1 OVERALL TRIAL DESIGN

This open label (OL), single group, long-term extension study of approximately 7 year duration, investigates the long term safety and efficacy of spesolimab in patients with perianal fistulas due to Crohn's disease who have completed treatment in a parent spesolimab trial. It is expected that a maximum of 20 patients will roll-over from study 1368-0008. Patients from other trials of spesolimab who meet the eligibility criteria may also be included in this trial in future and this will increase the number of participants.

Patients rolling over will be monitored for induction outcome at the EOT visit of the original trial and perform V1 of 1368-0007 at the same time, and initiate treatment upon availability of the MRI and endoscopy results.

Maintenance Treatment

Patients rolling-over into 1368-0007 trial must complete the treatment period in the preceding trial with an individual benefit (as per investigator's judgement).

The maintenance treatment in this study will be open-label and will evaluate one dose regimen (300mg s.c. q4w) of spesolimab. The trial will consist of a screening period lasting for a maximum of 14 days, followed by a 336 week maintenance treatment period and a 16 week safety follow-up period.

Proctoscopy or rectoscopy, as per routine clinical practice will be performed for all patients at EOT visit of the parent study and once every 48 weeks in this study to evaluate mucosal healing and to provide mucosal biopsy specimens for molecular pharmacodynamic assessments. Patients participating in the study will consent to undergo an ileocolonoscopy in case of a suspected flare. Full ileocolonoscopy/ colonoscopy or sigmoidoscopy instead of proctoscopy or rectoscopy could be performed if clinically indicated as per investigator judgement.

A schematic overview of trial design is shown in [Figures 3.1:1](#) and [3.1:2](#).

[figure not shown]

Figure 3.1:1 Trial design

Fistula relapse or luminal inflammatory flare treatment:

During this 7-year study, patients may experience worsening of their Crohn's disease either by experiencing a fistula relapse or a luminal inflammatory flare.

Fistula relapse is suspected if ≥ 1 external fistula orifice re-emerges, which was open at baseline or newly emerged during the preceding trial but was closed at completion of the parent study or at any time during the current trial; or which emerged newly. Fistula relapse is confirmed in a second independent visit ([Flowchart 2B](#)).

A patient with a confirmed fistula relapse will receive a single i.v. infusion of 1200mg spesolimab. At week 4 after the single i.v. infusion dose, patients will continue with an intensified subcutaneous spesolimab maintenance dosing of 600mg q4W, as seen in [Figure 3.1:2](#). An additional visit has to be planned at week 12 after the single i.v. infusion to check the patient's response status. For patients with fistula relapse, this week 12 assessment will include clinical assessment, [REDACTED] and MRI, which will guide investigator judgment of patient response status.

Luminal inflammatory flare, is defined as an increase in PRO-2 score [sum of 7-day weighted stool frequency (SF) and abdominal pain (AP) , components of the [REDACTED], using the original [REDACTED] multiplying factors of 2 for SF and 5 for AP] by >50 points from baseline of the current trial, plus an increase in [REDACTED] score by ≥ 100 points from baseline of the current trial with an absolute [REDACTED] >220 in a second independent confirmation visit, with an absolute [REDACTED], in absence of enteric pathogens in stool. In case of a suspected inflammatory flare, the site will ask the patient to immediately start entering his [REDACTED] symptom score data into the eDiary until the next scheduled or unscheduled visit at which a flare confirmation assessment will be performed, and then to continue entering the data as planned (i.e. for 10 days before each visit).

A patient with a luminal inflammatory flare (endoscopically confirmed) without fistula relapse might be treated as per SOC based on clinician judgement while continuing the same spesolimab maintenance dose according [flow chart 2A](#). After 12 weeks of flare confirmation (visit F3) a new rectoscopy/proctoscopy and [REDACTED] assessment will be performed to assess luminal flare response to SOC as per investigator judgement. For details of trial procedures, please follow the [Flow chart 2A](#).

Figure 3.1:2 Trial design in case of fistula relapse

[figure not shown]

Figure 3.1:3 Trial design in case of luminal inflammatory flare

Patients who are no longer deriving a clinical benefit will be required to discontinue treatment. See [Section 3.3.4.1](#) for details

Several interim analyses of PK, biomarker, and clinical data will be performed throughout the conduct phase of this study to support future trial applications, investigator brochures, regulatory documents, and scientific publications. The final analysis of the entire trial data will be performed once all patients have completed the last scheduled trial visit. The end of trial is defined as “last patient out”; i.e. last scheduled visit completed by last patient.

An independent Data Monitoring Committee is established to evaluate safety data of all ongoing spesolimab studies periodically, and to provide feedback on whether or not to continue the study with or without modifications.

3.2 DISCUSSION OF TRIAL DESIGN, INCLUDING THE CHOICE OF CONTROL GROUP(S)

Patients who complete treatment with spesolimab or placebo in parent trial and had individual health benefit from induction treatment will be offered to roll-over into this trial to receive long-term treatment with active drug.

This long-term study mainly aims to offer active maintenance treatment to patients who have benefited from induction treatment in a trial of spesolimab, and to characterize the safety and tolerability of spesolimab long-term treatment. It will also characterize the persistence of clinical outcome over a long period of spesolimab treatment and the efficacy of high dose rescue treatment for fistula relapses. Although a placebo control would improve this safety

and efficacy assessment, it would withhold patients in need from active treatment and is not justifiable for longer than the treatment period in the parent induction study. An active comparator is not suitable for this highly treatment-experienced and heterogeneous study population, where any approved treatment would have to be tailored towards the patient's individual treatment history. Moreover, patients responding to spesolimab induction treatment are likely to maintain their response on continued treatment with spesolimab, but to fail maintenance treatment if switched to a drug with a different MoA, which they may have failed in the past. Therefore, neither an active comparator nor placebo can be justified for this trial.

It is acknowledged that the reporting of data for this open-label, single-arm trial will likely be biased due to, among others, selection and reporting bias. This is, however, deemed acceptable given that all patients who derived an individual health benefit from previous induction treatment and who continued into this extension trial will be able to receive an active maintenance treatment with spesolimab for their ongoing disease.

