3.3.2 Inclusion criteria

Each patient must meet all of the following inclusion criteria to be included into the trial:

1. Patient older than 18 years
2. Has completed all treatments (placebo or active treatment) and the EOT visit in the parent induction trial in fistulising CD and is willing and able to continue treatment in 1368-0007.

3. Has obtained an individual health benefit, per investigator judgement (such as fistula response or remission or other clinical improvement), from treatment in the parent trial.
4. Signed and dated written informed consent for 1368-0007 in accordance with GCP and local legislation prior to admission into the trial.
5. Women of childbearing potential (WOCBP) must be ready to use highly effective methods of birth control per ICH M3 (R2) that result in a low failure rate of less than 1% per year when used consistently and correctly. A list of contraception methods meeting these criteria is provided in the patient information.

Note: A woman is considered of childbearing potential (WOCBP), i.e. fertile, following menarche and until becoming postmenopausal unless permanently sterile. Permanent sterilisation methods include hysterectomy, bilateral salpingectomy and bilateral oophorectomy. Tubal ligation is NOT a method of permanent sterilisation. A postmenopausal state is defined as no menses for 12 months without an alternative medical cause.

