3.3.3 Exclusion criteria

Patients meeting any of these exclusion criteria must not be enrolled into the trial:

1. Have experienced treatment-limiting adverse events during induction treatment with study drug.
2. Have developed any condition which meets the exclusion criteria from the original induction study.
3. Any condition which in the opinion of the investigator affects the safety or ability to participate in this trial.

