6. GENERAL ANALYSIS DEFINITIONS

6.1 TREATMENT(S)

For basic study information on treatments to be administered, assignment of treatment groups, and selection of doses, refer to CTP Section 4.

Patients who experience a fistula relapse during the maintenance treatment (as defined in CTP Table 2.1: 1) will be administered a single intravenous dose of spesolimab 1200 mg followed by an intensified subcutaneous maintenance dosing schedule with 600 mg q4w.

The following study periods are defined:

Table 6.1: 1 Flow chart of analysis periods which apply to all patients.

Analysis period	On-/off- treatmen t	Start (included)	End (included)
Screening period (Approx 1-2wks)	Off- treatment	Earliest of (Date of informed consent, first screening procedure)	Date/time of injection of first s.c. maintenance study drug minus 1 minute.
Overall maintenance period ¹ (Approx 336 wks)	On- treatment	Date/time of first s.c. maintenance study drug.	Date of last administered spesolimab (irrespective of formulation) + 112 days at 11:59pm.
Follow-up period ²	Off- treatment	Date of last study drug administration (irrespective of formulation) + 113 days at 12:00 AM.	Latest of: i) Date of EOS visit (Week 352 visit); ii) last contact date on End of Study page at 11:59 p m.

Dates are defined individually per patient. If more than one date is associated with a specific visit, measurements associated with a specific date are assigned to a study analysis phase according to the rules specified in the table. An analysis phase will not extend beyond the start date of the following phase.

The on-treatment period is defined as the overall maintenance period (including REP).

For all analysis periods, assessments done on the same day as the first maintenance treatment dose will be assigned to the appropriate analysis phase based on the assessment of date/time. If time is not collected for an assessment, then assignment will be to the previous analysis phase, e.g., to the screening phase.

Treatment Labels

Treatments will be labelled as follows:

"Overall Speso"

¹ The overall maintenance treatment period applies to all patients taking at least one dose of maintenance treatment regardless of flare occurrence. This period will be considered to understand long-term efficacy and safety of spesolimab.

² The follow-up period only exists if the trial completion date is after the date of end of last injection/infusion plus REP.

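### No planned safety summary in the public documents shows parent-trial arm, so the primary TEAE rate mixes first and continued exposure to spesolimab

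*Protocol*

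**What the plan says.** **Who enters.** Protocol 3.2 opens roll-over to "Patients who complete treatment with spesolimab or placebo in parent trial". Inclusion criterion 2 in 3.3.2 agrees: "Has completed all treatments (placebo or active treatment) and the EOT visit in the parent induction trial". Criterion 3, "Has obtained an individual health benefit, per investigator judgement", asks for benefit from parent treatment without naming an arm. Exclusion criterion 1 in 3.3.3 removes those who "Have experienced treatment-limiting adverse events during induction treatment with study drug".

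**How they are summarised.** SAP 6.1 defines a single treatment label, "Overall Speso", and a single on-treatment period: "The overall maintenance treatment period applies to all patients taking at least one dose of maintenance treatment regardless of flare occurrence". SAP 6.3 names one safety set as the main analysis set. SAP 5.1 starts time at risk for the primary endpoint at the first dose of this trial, not of the parent trial. SAP 7.8.1 tabulates AEs by treatment, system organ class and preferred term for the overall maintenance period only. SAP 7.7 tabulates time at risk and duration of exposure for the one pooled label.

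**What the benefit-risk text says.** Protocol 1.4.1 states: "Patients entering this trial will already have received a benefit from treatment with spesolimab in a preceding trial". Protocol 1.4 likewise limits the roll-over offer to patients who benefited from spesolimab in the parent study.

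**The concern.** The two groups differ by design at M1. Completing the parent trial without a treatment-limiting event says something about tolerance of spesolimab only for patients who received it. A placebo roll-over has not been tested on the drug, and any reaction to a first dose falls inside this trial's time at risk. Spesolimab roll-overs may also arrive with drug still present: Protocol 4.1.2 gives a half-life of about 4 to 5 weeks, and V1 is at parent EOT or at most 28 days later.

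The protocol gives the first two doses extra attention, with additional 60-minute vital signs at M1 and M2 (5.2.2). It also makes systemic hypersensitivity an AESI (5.2.6.1.4). Yet a reader of the planned tables could not see whether an early event followed a first or a later exposure, or how many of the patients in the denominator were new to the drug. The row for more than 0 to 48 weeks in the SAP 7.7 exposure table would combine patients with and without earlier spesolimab. What is at stake is how the primary safety result can be read.

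**Working it through.** The plan states no sample-size, power or rate figure for this point, so there is none to reproduce. Protocol 7.5 gives only up to 20 patients, from a parent cohort of 20.

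**1. What the primary rate averages.** Protocol 7.2.2 defines the rate as 100 × (patients with a TEAE) / (total time at risk). For a patient with an event, time at risk is ((onset − start) + 1)/365.25. Let R1 be the rate among placebo roll-overs, R0 the rate among spesolimab roll-overs, and w the placebo roll-overs' share of total time at risk. Then

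R_pooled = w × R1 + (1 − w) × R0.

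The pooled rate is interpretable without w only if R1 = R0. An event on the day of the first dose adds one case and (0 + 1)/365.25 = 0.0027 patient-years, so early events raise the numerator while adding almost nothing to the denominator.

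**2. Illustration with crude risks.** The allocation ratio, the number of placebo roll-overs and both risks are assumptions. With placebo share s, pooled risk = s × p1 + (1 − s) × p0.

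| Assumed first-exposure / continued risk | s = 1/3 | s = 1/2 |
|---|---|---|
| 30% / 10% | 10.0 + 6.7 = 16.7% | 15.0 + 5.0 = 20.0% |
| 20% / 5% | 6.7 + 3.3 = 10.0% | 10.0 + 2.5 = 12.5% |

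The same pair of risks gives a different pooled figure for each share, and neither component can be recovered from the table.

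**3. What a split could show.** Assume all 20 roll over, split 10/10 or 13/7 (spesolimab/placebo). With no events in n patients, the upper limit of the exact two-sided 95% interval is 1 − 0.025^(1/n):

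- n = 20: 16.8%
- n = 13: 24.7%
- n = 10: 30.8%
- n = 7: 41.0%

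The chance of at least one event at a true risk of 10% is 1 − 0.9^n: 88% for n = 20, 65% for n = 10 and 52% for n = 7.

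For comparison only, a two-sided 5% normal-approximation test of 30% against 10% would have power of about 19% (10/10) to 23% (7 first-exposure, 13 continued). A split therefore describes the groups and cannot compare them reliably.

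**4. The wording conflict.** Protocol 3.2 and 3.3.2 admit placebo completers. Protocol 1.4 and 1.4.1 describe entrants as having benefited from spesolimab. For a placebo roll-over both cannot be true. This needs no assumption.

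**The case against.** The strongest reply is that nothing is lost in the data. SAP 7 lists the individual values of all patients, 7.8.1 adds individual AE listings, and 4 and 7.5.2 add a fistula-status listing. A reader might infer from the single label that the two groups cannot be told apart at all. The documents do not support that: the gap is in the planned summaries, and parent arm can be attached to each patient. No visible text says that it will be, however.

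A reader might also infer that first-dose events come mainly from placebo roll-overs. No passage shows this. The exclusion criterion covers only treatment-limiting events, and Protocol 4.2.1.1 provides for patients who already had a mild-to-moderate infusion or anaphylactic reaction in the parent trial. Spesolimab roll-overs are thus not a reaction-free group.

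A third inference, that remission gained on placebo would be reported as spesolimab maintenance, no longer applies. SAP 2.0 drops both fistula proportions in favour of the listing. Even with a split, a trial without a control could not isolate drug benefit.

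It is also fair to say that:

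- starting the clock at M1 is declared and matches AE collection from the first extension dose;
- the analysis is descriptive, the trial was terminated early and the report is abbreviated;
- the protocol admits selection and reporting bias in general;
- several SAP sections are absent from the public text, so a parent-arm display there cannot be excluded.

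These points limit the concern to a modest one. They do not answer it for the AE tables, because SAP 7.8.1 lists only the overall period under the one label. The general admission of bias does not name the mix of parent arms.

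**Conclusion.** The point holds for the planned summaries. Both parent arms may enter, and the primary exposure-adjusted TEAE rate, the AESI tables and the exposure tables pool them from the first extension dose with no visible split. If first-exposure and continued-exposure risks differ, the pooled result depends on a mix the reader is not shown. On assumed risks of 30% and 10% it moves between 16.7% and 20.0% as the placebo share goes from one third to one half. That range indicates scale and does not estimate an effect in this trial: the allocation ratio, the number of placebo patients who entered and the true risks are not in the documents.

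The conclusion does not extend to the underlying data, to the source of early events or to efficacy. It does not invalidate the primary analysis; it is a cheap improvement in how that analysis is displayed. The conflict between Protocol 1.4/1.4.1 and 3.2/3.3.2 stands on the text alone.

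**What to change.** 1. In SAP 6.1 and 7.8.1, add parent-trial arm (spesolimab, placebo) as two descriptive columns beside "Overall Speso" in the overall TEAE table with the primary rate and in the AESI tables. Give the number of patients and time at risk in each column. Do the same for the exposure tables in SAP 7.7.
2. Add parent arm as a variable in the AE listings and in the fistula-status listing. This matters for the latter because the efficacy baseline (SAP 5) is that of the parent trial, so change during a placebo phase is carried in.
3. State that the split is descriptive, with no comparison between columns.
4. Reconcile Protocol 1.4 and 1.4.1 with 3.2 and 3.3.2 on what entrants received and benefited from, or note the discrepancy in the report.

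The cost is a few table columns and one listing variable. Parent-arm data were probably obtainable: the SAP history table cites parent-trial efficacy results and dates this revision before final database lock. The downside is very small groups with wide intervals, for example an upper limit of 41.0% for no events in 7 patients. If the columns are judged too sparse for an abbreviated report, the listing variable alone would still let a reader separate first from continued exposure.
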